For the HANSE trial, 5,000 participants aged 55-79y who meet the NELSON and/or PLCO_{M2012} 6 year risk >1.58% selection criteria will be included. Participants will undergo baseline and 1-year screening under defined conditions using low-dose computed tomography in three specialized lung cancer centers in northern Germany.

Standardized and quality-assured image analysis will be conducted using state-of-the-art artificial intelligence (AI)-based detection and nodule measurement software (AVIEW, Coreline Soft Company Ltd., South Korea) to support the radiologist. CT assessment of lung nodules will be done according to LungRADS 1.1 criteria, as well as volume doubling time according to the European position statement on lung cancer screening (14). Additionally, this trial integrates different recruiting strategies, a smoking cessation counselling program, includes a cost-effectiveness modelling, cardiovascular and lung comorbidity assessment, different lung nodule management strategies (Lung RADS 1.1. vs. PanCan vs. AI) and explores blood-based biomarkers in positive LDCT cases.

An additional objective of the HANSE study is to provide evidence for the potential of low dose CT in the diagnosis of diseases other than lung cancer, such as emphysema, but also cardiovascular diseases, which to date has only been suggested by retrospective analyses of LDCT studies (15, 16). Low dose CT does allow to examine the coronary calcium score (Agatston score (17)), indicative of the coronary plaque status which has shown to correlate with the rate of future myocardial infarction, stroke and death due to cardiovascular disease (18). The trial will assess whether reporting of the score may have consequences in individuals with a positive

coronary calcium score seeking specialist consultation and initiating preventive cardio-vascular therapy.

The trial will further encompass a smoking cessation program and smoking cessation rate under the different experimental settings will be determined at 1-year follow-up. Specifically, the consequences on smoking status will be compared between the non-reporting group, the calcium score reporting group, the emphysema score reporting group vs. the non-reporting group in order to document a potential impact of reporting.

Additionally, this design feature allows to analyse long-term smoking cessation rates and mortality in a follow-up study at year 5 and 10 (not part of this funding period).

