5.2.2 Adjustment for Multiple Comparisons

The primary and key-secondary endpoints will be tested in a hierarchical order, thereby controlling the overall type-I error rate at 5%. Therefore, no correction of p-values for multiple testing needs to be performed. All secondary parameters will be considered explorative.

Strengths and Limitations

Strengths

Importantly, the results and the innovative workflow infrastructure of this study should pave the way for an effective comprehensive screening program in Germany. Especially, novel results about the definition of the high-risk population, the inclusion of cardiovascular and lung comorbidity, smoking cessation and cost-effectiveness will guide the future German lung cancer screening program.

Limitations:

This study is designed as a reference case for a nationwide lung cancer screening program, which both suffer from limitations. The voluntary participation may introduce a certain bias and may not reveal all high-risk cases. In addition, clinically not apparent lung cancer cases in the low-risk population will be missed, since this group will not receive a LDCT. However, we follow-up smokers, who did not meet the risk score inclusion criteria and were willing to participate in the study, after 5 years to calculate the proportion of clinically detected lung

cancers, which were missed due to non-inclusion in the high risk group. This will generate important data for the ethical and economical discussion of risk-based inclusion for lung cancer screening.

The assessment of coronary calcium scores is usually performed on normal dose ECG-gated CT. However, recently it has been shown that coronary artery calcium scoring is feasible on non-ECG-gated LDCT. Furthermore, the used Coreline software has an innovative and fully automated algorithm especially developed for non-ECG gated Coronary calcium score on LDCT.

Due to the 36 month time horizon of the study, the endpoint ‘initiation of cv treatment’ was selected, rather than a clinically more meaningful endpoint, such as 10 year cardiovascular mortality, for example. However, the investigators will seek additional funding to continue the coronary calcium part of the study in order to evaluate cardiovascular and all-cause mortality at year 10 follow-up.

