For the HANSE study the calibrated threshold for the PLCO 5 year risk score of 1,314% was converted to a 6year threshold of 1,58% , because the original PLCO risk score calculates the 6year risk and thus the original calculators by Tammemägi et al. can be used for the HANSE study (13).For this conversion linearity between year 5 and 6 was assumed.

(ii) Sample size for the evaluation of **initiation of cardiovascular therapy** within 1 year after randomization has been calculated using Chi-Square Test and two-sided type-I-error rate of 5% based on the results of the ITALUNG study (15,16), where for 44% of all patients coronary artery calcification (CAC) was detected. In the ITALUNG study, 63% of patients with CAC were on cardiovascular treatment without receiving results of their low dose CT screening. For this study, where the patients are randomized to either reporting or non-reporting of CT screening results, we conservatively assume that the non-reporting group shows a rate of cardiovascular treatment of 68%. In contrast, as an effect of reporting the screening results, we assume that in the reporting group 73% of patients receive cardiovascular treatment, so the effect of reporting the CT results is assumed to be an increase of 5 percentage points in the cardiovascular treatment rate. Acknowledging that only 44% of all patients are assumed to show CAC on low dose CT, the expected difference between the reporting and non-reporting group is $(73\% - 68\%) * 44\% = 2.2\%$. Equivalently, the assumed rate ratio between the reporting and non-reporting group is $(73\% * 44\%) / (68\% * 44\%) = 1.07$. With 2,500 patients randomized to each arm and using a Chi-Square Test with a two-sided type-I-error rate of 5% for testing the null-hypothesis of no difference between the groups, the statistical power is 97%.

(iii) To evaluate the power of potential **longitudinal follow-up** studies based on this screening trial, the power for the 10 year mortality endpoint has been calculated based on the results of the NELSON study using a Chi-Square Test with a two-sided type-I-error rate of 5% for testing the null-hypothesis of no difference in 10-year cardiovascular mortality rates between the

reporting and non-reporting groups. In line with the results of the NELSON study, we assume a 10 year cardiovascular mortality rate in the non-reporting group of 2.7%.

[figure not shown]

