Assuming a rate ratio of 0.6 between the reporting and non-reporting group (or equivalently, a 10-year mortality rate of 1.6%), the difference between the reporting and non-reporting group can be shown with a power of 75%.

Conclusion: With an overall sample size of 5,000 subjects (and 2,500 volunteers randomized to the reporting and non-reporting group) the study is well-powered to investigate the primary hypothesis, evaluate potential cardiovascular benefit and provide the basis to investigate mortality in a follow-up study.

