smoking cessation program. A team of clinical and health economic experts will define the detailed structure of the model.

- **Outcome analyses:** For each screening scenario, a Monte Carlo simulation (MCS) with 1,000 iterations will be performed to estimate expected outcomes and MSC-based confidence intervals. Primary outcomes of the analysis are long-term all-cause mortality, additional costs per quality-adjusted life year (QALY) gained, per life year (LY) gained or per death averted. Efficiency frontiers will be constructed for each primary outcome to identify efficient screening scenarios and calculate the incremental cost-effectiveness of these scenarios. The impact of variations in the values of key input parameters (adherence to screening, smoking cessation etc.) on model outcomes will be tested in sensitivity analyses.

Consequences of screening:

- All screened individuals will ask to participate in a 'Consequences of Screening' survey in order to evaluate their emotional and psychological condition during the screening process. Survey will be based on the psychological consequences questionnaire, adapted for lung cancer screening (19).
- In addition, the patient questionnaire will evaluate the socioeconomic background, smoking cessation, lung and cardiovascular health.
- The exact questions of the questionnaire will be determined before the study start and included in the appendix of the protocol.
- GP contact information is recorded.
- Current medication is recorded.

3. LDCT 1 year - 2. Screening round

Timing of the follow-up chest CT according to LungRADS 1.1 schedule.

Chest LDCT scan procedure and image analysis as in the 1st screening round.

- **Lung LDCT assessment:** Assessment of newly identified lung nodules will be done according to LungRADS 1.1 criteria. Follow-up radiographic assessment of solid nodules will be based upon volume doubling time (VDT) as a key driver for recommendations on further course of action.
- **Lung function test:** All included participants will receive a lung function test prior to undergoing LDCT.

- **Cardiovascular health:** All participants will be questioned whether they initiated treatment for any cardiovascular conditions during the study. Blood pressure, heart rate, and BMI data will be obtained.
- Additionally, the study is designed to analyze cardiovascular events and mortality in a follow-up study at year 5 and 10 (not part of the current funding period).

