- **Assessment of smoking status:** Success of the smoking cessation program will be evaluated using a questionnaire, combined with a urine cotinine check (in quitters).
- **Initiation of COPD treatment:** Assessment of COPD treatment initiation during the study.
- **Consequences of screening:** Questionnaire 'Consequences of Screening' as above.

2. Evaluation

Lung cancer screening:

- The percentage of subjects receiving an adequate low-dose CT scan according to DRG guidelines will be assessed.
- For all included participants, detection rate of lung cancers will be evaluated and categorized according to LungRADS 1.1 categories.
- Detected (proven by histopathology) lung cancers will be categorized whether they were predicted by PLCO or NELSON or both. Statistical analysis will reveal potential advantages of either risk scoring methodology.
- A retrospective analysis will compare this algorithm to the PanCan nodule algorithm vs. AI for management efficiency. Based on the two alternative management algorithms patients are sorted into three management groups: (a) next surveillance scan, (b) early recall scan, or (c) diagnostic evaluation recommended. For one algorithm to be more efficient, the following criteria must both be fulfilled
 - The number of patients without lung cancer sorted in the category (a) is higher AND
 - The number of patients with lung cancer sorted into category (b) or (c) is higher.

Coronary calcium score / cardio-vascular treatment initiation:

- At the 1-year follow-up visit, the rate of initiation of cardiovascular treatment (in particular lipid-lowering) will be determined, together with BMI, and blood pressure data. Data for the calcium score reporting group will be compared to those of the non-reporting group.

Smoking cessation:

- Success of smoking cessation counseling will be based on the number of participants quitting (% quitters) within study period.
- Allocation of the participants to the different experimental groups will allow determining the influence of 'reporting' of prognostic markers (percent emphysema and coronary calcium score) on smoking cessation.

All methods will be performed according to study site SOPs.

CT analysis software (Coreline) specifications:

1. Viewer function

- LCS (Lung Cancer Screening) viewer functions

- Image display with axial, sagittal and coronal images and 3D rendering.
- Virtual slice thickness control display function for MPR (Multi-Planar Reformat) images.

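### The 97% power stated for the cardiovascular-treatment endpoint contradicts the 2.2-point difference derived just before it; on the plan's on-treatment rates the power is about 39% in all randomised, or 73% in CAC-positive participants only

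*Protocol*

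**What the plan says.** Protocol section 5.3 (ii), repeated in the synopsis under Statistical Analysis (ii), sizes the comparison of cardiovascular therapy within one year of randomisation. The calculation "has been calculated using Chi-Square Test and two-sided type-I-error rate of 5% based on the results of the ITALUNG study". That study supplies a CAC prevalence of 44%, and a treatment rate of 63% among CAC-positive patients who were not told their result. For this trial the protocol assumes 68% on treatment without reporting and 73% with reporting.

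It then dilutes the effect: "Acknowledging that only 44% of all patients are assumed to show CAC on low dose CT", the expected difference between arms becomes (73% − 68%) × 44% = 2.2 points, and the rate ratio 1.07. The next sentence takes 2,500 randomised per arm and concludes, for the null hypothesis of "no difference between the groups, the statistical power is 97" per cent. The closing conclusion of 5.3 says that "the study is well-powered to investigate the primary hypothesis, evaluate potential cardiovascular benefit".

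Elsewhere the endpoint is described as initiation. In section 6.1.2, at the second screening round, "All participants will be questioned whether they initiated treatment for any cardiovascular conditions during the study"; under Evaluation, "the rate of initiation of cardiovascular treatment (in particular lipid-lowering) will be determined". Section 1.2 describes the aim in terms of CAC-positive people: "The trial will assess whether reporting of the score may have consequences in individuals with a positive" coronary calcium score. Section 5.2.2 states: "All secondary parameters will be considered explorative".

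**The concern.** With arms of 2,500 and rates near 30%, a difference of 2.2 points is less than two standard errors, so power close to 97% is not credible. The figure looks like the power for the undiluted 5-point effect, applied to the whole randomised sample although the paragraph has just said that the effect arises in only 44% of it. The rate ratio cannot expose this, because the 44% cancels from numerator and denominator.

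Sections 2.2 and the synopsis place this endpoint under the main secondary objective, and it supports one clause of the well-powered conclusion. A reader who believes the power is 97% would take a null result as strong evidence that reporting the score does not change treatment. If the true figure is near 39%, a null result would say little.

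A second mismatch is that the inputs are proportions on treatment, whereas the endpoint is the proportion who start treatment.

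**Working it through.** **Inputs (section 5.3 (ii) and synopsis).** Chi-square test, two-sided 5%; 68% and 73% on treatment; CAC prevalence 44%; 2,500 per arm. The synopsis recruits 5,500 to retain 5,000, so 2,500 per arm is already net of the 10% dropout.

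**Formula.** Power = Φ[(|p₁ − p₂| − 1.96·s₀)/s₁], with s₀ = √(2·p̄(1 − p̄)/n), p̄ the mean of the two rates, and s₁ = √((p₁(1 − p₁) + p₂(1 − p₂))/n).

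**1. Reproducing the stated figure.** 68% vs 73%, n = 2,500: s₀ = 0.01290, s₁ = 0.01288. (0.05 − 1.96 × 0.01290)/0.01288 = 1.92, so power = 97.3%. This matches the protocol, with the 44% not applied.

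**2. The plan's own diluted difference.** 0.68 × 0.44 = 29.92%; 0.73 × 0.44 = 32.12%; difference 2.2 points; n = 2,500: s₀ = s₁ = 0.01308. (0.022 − 1.96 × 0.01308)/0.01308 = −0.28, so power = 39.0%.

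**3. CAC-positive participants only.** 0.44 × 2,500 = 1,100 per arm; 68% vs 73%: s₀ = 0.01945, s₁ = 0.01942. (0.05 − 1.96 × 0.01945)/0.01942 = 0.61, so power = 73.0%.

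Simulation with 200,000 runs per scenario agrees with all three (97.3%, 39.0%, 73.1%).

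**Could another convention give 97% for the 2.2 points?** No:

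| Variant, 29.92% vs 32.12% | Power |
|---|---|
| One-sided 5% | 51.5% |
| Continuity-corrected | 37.9% |
| Arcsine | 39.0% |
| 2,750 per arm | 42.2% |

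**Treated CAC-negative participants.** The diluted rates count no treated CAC-negatives. Adding them at an equal assumed rate r in both arms (0.56·r added to each) keeps the difference at 2.2 points. Power is 39.0% at r = 0, 34.4% at 30%, 35.3% at 50% and 39.1% at 68%.

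**Check of the method.** The same formula applied to the neighbouring mortality calculation in 5.3 (iii), 2.7% vs 2.7% × 0.6 = 1.62% with 2,500 per arm, gives 74.8% against the stated 75%.

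**Size of the gap.** For 80% power the 2.2-point difference needs about 6,939 randomised per arm. A CAC-positive comparison needs about 1,305 per arm, that is 1,305/0.44 ≈ 2,966 randomised per arm. With 2,500 per arm, the difference detectable with 80% power in all randomised is 3.7 points, equivalent to 3.69/0.44 = 8.4 points among CAC-positives, against the 5 assumed.

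**The case against.** The strongest objection is that no analysis of on-treatment rates is planned: the endpoint is initiation, with treatment status asked at baseline and new treatment asked at one year. If the 63% from the source study is taken as a baseline and subtracted, new starts are 5% vs 10% of CAC-positives, or 2.2% vs 4.4% of all randomised. That is also a 2.2-point difference, but at low rates. Power is then 99.2% with 2,500 per arm (99.4% in 1,100 CAC-positives per arm). If CAC-negatives also start treatment at an assumed 2%, 5% or 10% in both arms, it falls to 96.6%, 90.2% or 78.0%.

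What stands is that power for initiation may well be adequate, so the trial cannot be called underpowered for its named endpoint. It also follows that 39% or 73% must not be printed as the power for initiation. But this reading does not rescue the stated figure. The protocol never subtracts 63%, and its ratio of 1.07 is a ratio of on-treatment rates; for new starts the ratio would be 2.

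Two lesser objections have some force. Section 5.3 does point to all randomised participants, since it uses 2,500 per arm, and section 1.2 is background; the doubt about the population is modest. And the endpoint is explorative, outside the tested hierarchy, so the consequence is limited to what the protocol claims for it.

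**Conclusion.** The concern holds. The stated 97% belongs to a 5-point effect in every randomised participant, which the same paragraph rules out. On the protocol's own on-treatment rates the power is 39% in all randomised (34% to 39% if CAC-negatives are treated equally in both arms at an assumed 0% to 68%), or 73% in CAC-positives only. In the all-randomised comparison the assumed effect would be missed about 6 times in 10.

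These figures rest on the stated 68%, 73% and 44%, a two-sided 5% chi-square test, and 2,500 analysed per arm. For initiation of treatment the protocol states no rates, and the power ranges widely with what is assumed. The cardiovascular part of the well-powered conclusion is therefore unsupported as written, rather than shown to be false. This should be fixed, but it does not touch the primary PPV comparison or the sample size of 5,000.

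**What to change.** In section 5.3 (ii) and the matching synopsis text:

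- State whether the comparison is made in all randomised or in CAC-positive participants, and whether the quantity is being on treatment or newly starting it.
- If the endpoint remains initiation, recalculate with explicitly assumed initiation rates in each arm, including CAC-negative participants if all randomised are compared, and show a range. This is the route that matches the endpoint definition.
- If on-treatment rates are kept, label them as such and replace 97% with 39% (all randomised) or 73% (CAC-positive only).

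In the conclusion of 5.3 and of the synopsis, qualify only the cardiovascular clause and note that the endpoint is explorative.

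The cost is one rerun calculation and a few sentences. If on-treatment rates are kept, the printed figure becomes less favourable. Sample size, data collection and the primary analysis stay as they are.

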6. STUDY CONDUCT AND REGULATORY DETAILS

6.1 Data Management

6.1.1 Study Flow Chart and Plan

* Follow-up schedule

LungRADS Categories:

- 1, 2: 1 year LDCT
- 3: 6 months LDCT; VDT assessment
- 4a: 3 months LDCT; VDT assessment
- 4b, X: MDT, tissue sampling depending on the probability of malignancy and comorbidities.

Figure 1: Flow diagram of the HANSE study.

6.1.2 Procedures

Figure 2: Procedure workflow of the Hanse Study

1. Recruitment

- Population will be contacted by mail (address data of individuals in the age group obtained from local population registries) with an **individually tailored invitation letter** and response element (paper and website) to assess their overall qualification and willingness to participate. Additional recruitment efforts via local physicians (**GPs**), and via **public media** using the study website.

Age	
Gender	
Race/ethnicity	
Education	
Height	
Weight	
Chronic obstructive pulmonary disease (yes vs. no)	
Prior diagnosis of pneumonia (yes vs. no)	
Prior diagnosis of emphysema (yes vs. no)	
Prior diagnosis of bronchitis (yes vs. no)	
Prior diagnosis of tuberculosis (yes vs. no)	
Personal history of cancer (yes vs. no)	
Family history of lung cancer (yes vs. no)	
Early onset vs. late onset	
Smoking status (former=0, current=1)	
Former smoker (yes vs. no)	
Current smoker (yes vs. no)	
Smoking intensity (average cigarettes/day)	
Smoking duration (years)	
Smoking quit-time	
Chest CT within past year (yes vs. no)	
Pregnancy yes/no	
Any comorbidities (free text)	
Ability to travel to the screening center	

Table 5: Variables for risk scoring, applicable for PLCO model

- Initial eligibility assessment based on self-reported data (age, smoking history and parameters required for the NELSON inclusion criteria and PLCO scores, table 5) in return letter, based on individuals' input in study website, or according to GP assessment. Data of eligible subjects will be stored in CRO database. Eligible subjects (based on initial assessment of risk) will receive an invitation for participation in the screening program with additional background information.
- On site validation of variables required for risk scoring models and accompanying assessment of medical condition, medical history, current medication by qualified medical staff.
- Data will be stored in database (CRO) and PLCO_{M2012} risk score and NELSON inclusion criteria will be determined. Individuals with PLCO_{M2012} risk score $\geq 1.58\%$ (6 yrs.) or NELSON inclusion criteria will be included in the study.
- Non-qualifying subjects (who did not meet the NELSON inclusion criteria or PLCO criteria) will be asked to volunteer by contributing long-term outcome data informing of the development of lung cancer or death from lung cancer. In addition NELSON and PLCO non-qualified subjects with a smoking history, who volunteered to participate in the HANSE study, will be contacted via mail after 5 years to inquire if they developed lung cancer in the time between their recruitment and present. Non-responders will be followed by local cancer registries and by phone.

2. **LDCT - 1. Screening round**

- **Lung function test:** All included participants will receive a lung function test prior to undergoing LDCT.
- **Cardiovascular health:** All participants will be questioned whether they receive treatment for any cardiovascular conditions. Blood pressure, heart rate and BMI data (height and weight) will be obtained.
- Assessment of current **COPD treatment medication.**
- **Randomization:** Subjects included in the screening study will be randomized prior to receiving the initial LDCT scan. Randomization will not affect the procedure and the schedule of the cancer screening process but only determine the allocation of the participants of the coronary calcium score and emphysema score to the reporting and the non-reporting group. Randomization ratio of 1:1 and a 2-factorial design ($\frac{1}{4}$ calcium score only; $\frac{1}{4}$ emphysema score only, $\frac{1}{4}$ both; $\frac{1}{4}$ none) will provide equally sized groups of patients in both groups including age (5 year groups) and sex stratification .

Lung LDCT assessment:

- **Standardized and quality-assured image analysis** will be conducted using state-of-the-art artificial intelligence (AI)-based detection and nodule measurement software (Coreline) to support the radiologist. CT assessment of lung nodules will be performed according to LungRADS 1.1 criteria (see Appendix), as well as volume doubling time according to the European position statement on lung cancer screening (14).
- Inspection of **lungs for nodules** will be carried out for all subjects, independent of the assigned groups (reporting or non-reporting).
- An independent 2nd read by an additional radiologist using the same reading software algorithm will be performed.
- Subjects with no nodules or those of LungRADS grades 1, 2, 3, 4a will be scheduled for follow-up scans at intervals according to LungRADS schedule (see Appendix).
- Findings categorized as LungRADS Cat. 4b or 4X nodules will be presented to the local Multidisciplinary Tumor Board (MDT) for further assessment and treatment decisions in the clinical routine workflow.
- **Emphysema** severity as a measure for tobacco related lung destruction will be quantitatively assessed on the LDCT images using the fully automated artificial intelligence (AI)-based algorithm of the Coreline software (Coreline, Seoul South Korea). The data will either be reported to study participants and treating physicians or not according to the allocation of the individual to the two randomized experimental groups.
- **Coronary calcium scores** (Agatston score) will be assessed using the fully automated artificial intelligence (AI)-based algorithm of the Coreline software (Coreline, Seoul South Korea). However, only the reporting group will receive the results of the score, together with an explanation of potential consequences of these findings for their cardiovascular health and with recommendation to seek specific consultation with their general practitioner or specialist. In this group a report is sent to the participants' GP.
- The LDCT image data, the coronary calcium score and % emphysema of the non-reporting group will remain confidential and will be stored for further assessment at year 1 (follow-up CT screen) and for evaluation of endpoints at year 5 and 10 (not part of this funding period).
- Apart from the randomized reporting of coronary artery calcium score and % emphysema **clinically relevant incidental findings** will be categorized in emergent (within 1-30 days), timely (within 1-6 months) or regular (>6 months) follow up. They will always be included in the CT report for the study participants.

- For emergent findings the study participant will be contacted directly by the local study team.
- Clinically non-relevant CT findings (i.e. liver or kidney cysts) not requiring physician consultation will not be included in the report.

Smoking cessation program:

- Prior to obtaining the chest CT, all participants are counselled for smoking cessation and referred to a smoking cessation program, according to the requirements defined by the Joint Statement of the German Radiological Society. Specifically, participation in local certified smoking cessation programs such as “Das Rauchfrei Programm” (<https://www.mhh.de/pneumologie/rauchfrei>) is encouraged. In addition, an information brochure about smoking cessation and available local certified smoking cessation programs and further online information material will be given to each participant.

Biomarker program:

- All patients undergoing tissue sampling according to the LungRADS 1.1. criteria will be invited to participate in the translational biomarker program using a separate informed consent form. For the program, a blood sample for epigenetic profiling will be required, together with an exhalation sample for assessment of specific exhalatory transition markers. The findings of the Biomarker analysis will be correlated to the pathological results of the radiological finding. The exact biomarkers will be determined before the study start and included in the appendix of the protocol.
- Optionally, blood samples will be collected from the high-risk group at the 1st and 2nd screening round visit and stored in the DZL biobank for future research.

Long-term performance and cost-effectiveness:

- The Center for Health Economics Research Hannover (CHERH) develops a comprehensive microsimulation platform for the assessment of long-term performance and cost-effectiveness of nationwide lung cancer screening with LDCT based on the HANSE study data. Main objectives of the modelling study are to investigate the impact of different components of LDCT lung cancer screening on the long-term all-cause mortality and cost-effectiveness. Key components include risk score-based selection criteria, nodule management protocols, threshold values of imaging biomarkers for cardio-vascular diseases and COPD, and inclusion of smoking cessation programs.
- **Model concept:** The stochastic microsimulation model simulates virtual life histories of the HANSE study, which represents a representative sample of the German population in northern Germany. For each individual, it creates different life histories: no LC-screening, LC-screening focussing on lung cancer only, LC-screening including cardiovascular and lung comorbidity assessment, comprehensive LC-screening plus

smoking cessation program. A team of clinical and health economic experts will define the detailed structure of the model.

- **Outcome analyses:** For each screening scenario, a Monte Carlo simulation (MCS) with 1,000 iterations will be performed to estimate expected outcomes and MSC-based confidence intervals. Primary outcomes of the analysis are long-term all-cause mortality, additional costs per quality-adjusted life year (QALY) gained, per life year (LY) gained or per death averted. Efficiency frontiers will be constructed for each primary outcome to identify efficient screening scenarios and calculate the incremental cost-effectiveness of these scenarios. The impact of variations in the values of key input parameters (adherence to screening, smoking cessation etc.) on model outcomes will be tested in sensitivity analyses.

Consequences of screening:

- All screened individuals will ask to participate in a 'Consequences of Screening' survey in order to evaluate their emotional and psychological condition during the screening process. Survey will be based on the psychological consequences questionnaire, adapted for lung cancer screening (19).
- In addition, the patient questionnaire will evaluate the socioeconomic background, smoking cessation, lung and cardiovascular health.
- The exact questions of the questionnaire will be determined before the study start and included in the appendix of the protocol.
- GP contact information is recorded.
- Current medication is recorded.

3. LDCT 1 year - 2. Screening round

Timing of the follow-up chest CT according to LungRADS 1.1 schedule.

Chest LDCT scan procedure and image analysis as in the 1st screening round.

- **Lung LDCT assessment:** Assessment of newly identified lung nodules will be done according to LungRADS 1.1 criteria. Follow-up radiographic assessment of solid nodules will be based upon volume doubling time (VDT) as a key driver for recommendations on further course of action.
- **Lung function test:** All included participants will receive a lung function test prior to undergoing LDCT.

- **Cardiovascular health:** All participants will be questioned whether they initiated treatment for any cardiovascular conditions during the study. Blood pressure, heart rate, and BMI data will be obtained.
- Additionally, the study is designed to analyze cardiovascular events and mortality in a follow-up study at year 5 and 10 (not part of the current funding period).
- **Assessment of smoking status:** Success of the smoking cessation program will be evaluated using a questionnaire, combined with a urine cotinine check (in quitters).
- **Initiation of COPD treatment:** Assessment of COPD treatment initiation during the study.
- **Consequences of screening:** Questionnaire 'Consequences of Screening' as above.

2. Evaluation

Lung cancer screening:

- The percentage of subjects receiving an adequate low-dose CT scan according to DRG guidelines will be assessed.
- For all included participants, detection rate of lung cancers will be evaluated and categorized according to LungRADS 1.1 categories.
- Detected (proven by histopathology) lung cancers will be categorized whether they were predicted by PLCO or NELSON or both. Statistical analysis will reveal potential advantages of either risk scoring methodology.
- A retrospective analysis will compare this algorithm to the PanCan nodule algorithm vs. AI for management efficiency. Based on the two alternative management algorithms patients are sorted into three management groups: (a) next surveillance scan, (b) early recall scan, or (c) diagnostic evaluation recommended. For one algorithm to be more efficient, the following criteria must both be fulfilled
 - The number of patients without lung cancer sorted in the category (a) is higher AND
 - The number of patients with lung cancer sorted into category (b) or (c) is higher.

Coronary calcium score / cardio-vascular treatment initiation:

- At the 1-year follow-up visit, the rate of initiation of cardiovascular treatment (in particular lipid-lowering) will be determined, together with BMI, and blood pressure data. Data for the calcium score reporting group will be compared to those of the non-reporting group.

Smoking cessation:

- Success of smoking cessation counseling will be based on the number of participants quitting (% quitters) within study period.
- Allocation of the participants to the different experimental groups will allow determining the influence of 'reporting' of prognostic markers (percent emphysema and coronary calcium score) on smoking cessation.

All methods will be performed according to study site SOPs.

CT analysis software (Coreline) specifications:

1. Viewer function

- LCS (Lung Cancer Screening) viewer functions

- Image display with axial, sagittal and coronal images and 3D rendering.
- Virtual slice thickness control display function for MPR (Multi-Planar Reformat) images.
- Semi-automatic nodule segmentation and measurement.
- Follow-up nodule comparison, using automatic nodule position registration.
- Quantitative feature calculation from the nodule segmentation.
- Calculation of VDT (volume doubling time) and cancer-risk probability based on PANCAN model (Brock model).
- Structured reporting UI based on Lung RADS v1.1, with incidental findings (S Modifier) (Can be modified to conform to German requirements)
- Form-based report generation

- LAA (Lower Attenuation Area) viewer functions

- Lobe-based quantitative emphysema analysis, such as LAA-950HU and Perc15.
- Image display of axial, sagittal, coronal and 3D rendering, with LAA mask overlaid.
- Bull's eye chart for displaying LAA distribution in lobes, which are automatically segmented.
- Histogram analysis of lung parenchymal densities.
- Form-based report generation

- CAC (Coronary Artery Calcification) viewer functions

- Automatic calcification labeling and manual correction.
- AGATSTON scoring and isotropic volume scoring.
- Form-based report generation

- Automatic processing server (APS) engines

- Lung nodule detection engine (CADe, for research purpose only till CE certification)
- Lung/lobe segmentation engine for automatic nodule position determination.
- LAA analysis engine
- CAC analysis engine

- Worklist functions

- Display the important results in separate columns; (Lung-RADS category, LAA-950HU, CAC, etc.)
- Workflow management to enable double-reading capability.
- Automatic notification of high-risk (critical) reading results.
- Exporting results in CSV format (MS-Excel compatible)

2. Central registry function

- Anonymization of uploaded patient data.
- Web-based questionnaire (Specific requirements must be determined.)
- Collects all the reading results in the CLOUD database.
- CT dose management, using dose report from CT devices.
- Dashboard view to display all participating hospitals' information (charts and tables).

3. Additional function support further research work

- Radiomics feature generation from the segmented nodules.
- Exporting all the collected information in CSV format (MS-Excel compatible).
- Exporting nodule segmentation masks.
- Interface with 3rd-party research modules, such as nodule malignancy estimation.

4. Function be customized in the preparation phase of the HANSE study

- German language support.
- Customization to reflect German workflow.
- Customization of structured reporting for incidental findings.
- Development of web-based questionnaire system.
- Development of nodule management system including dashboard
- Interface with existing PACS, RIS and EMR

